Incidence; duration each episode									•	•	•	•
Average & worst wound pain									•	•	•	•
Incidence; duration each episode									•	•	•	•

Difficulty sleeping due to pain?	•	•	•	•	•	•	•				
Awakenings due to pain	•	•	•	•	•	•	•				
Nausea (0=none, 10=vomited)	•	•	•	•	•	•	•				

* In addition to the above, for knee and shoulder surgery joint range of motion will be measured at various time points between 1-12 months as part of standard postoperative care; and for VATS, FEV1 will be measured at various time points during hospitalization as part of standard postoperative care.

Statistical Analysis. The limb amputation, total knee and shoulder arthroplasty, rotator cuff repair, VATS, and skin grafting subjects will be included in pilot studies to help power future clinical trials, so we will enroll a convenience sample and not have a pre-determined primary endpoint or statistical plan. However, the end points of most interest will be average pain score on postoperative day 2 for shoulder arthroplasty and skin grafting subjects, range-of-motion at 6 weeks for the rotator cuff repairs, range-of-motion for knee arthroplasty, and FEV1 for the VATS procedures.

For the subjects having mastectomy, we will power this study for an acute pain end point which will provide conclusive results for that end point; but, the data will also be used to help power a subsequent large, multicenter clinical trial for a chronic pain-related end point (which will require far more subjects than we will enroll for the current study).

For the mastectomy subjects, sample size calculations are centered around the hypothesis that cryoneurolysis decreases the incidence and severity of post-mastectomy pain in the week following surgery. To this end, the primary outcome is the average NRS (as administered as part of the Brief Pain Inventory) queried on the afternoon of postoperative day 2. The difference in the distribution of NRS between groups will be assessed using the Mann-Whitney U test. We approximate power using the two-sample t-test. Assuming a standard deviation of 2.25 NRS points,² and minimum clinically meaningful difference of 2 NRS points, n=30 patients per group provide 86% power with two-sided $\alpha=5\%$.

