The t-test approximation was confirmed by simulating integer valued NRS scores in the range 0 to 10. One group was simulated by rounding normally distributed data with mean 1.5 and standard deviation 2.5 (resulting in median of 2 and interquartile range 0 to 3); and the other with mean 3.5 and standard deviation 2.5 (resulting in median of 4 and interquartile range 1 to 5). Note these resulting summary statistics are consistent with Ilfeld et al (2014). When 10,000 trials were simulated under these assumptions, the Mann-Whitney U test provided 89.5% power, and Type I error was maintained at 4.85%.

Differences between groups in demographic variables and secondary endpoints will be assessed with the Mann-Whitney U test for continuous or ordinal data, and Fisher's Exact test for categorical data. Box-and-whisker plots will be used to visualize distributions by group.

R version 3.4.4 ([R-project.org](https://www.R-project.org)) was used for sample size calculations and simulations; and the most recent version of R will be used at the time of analysis.

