17. POTENTIAL BENEFITS

For subjects randomized to receive a sham treatment: There will be no difference between being in this study and deciding against participation. Therefore, there is no potential for direct benefits from this sham "treatment".

For subjects randomized to receive active cryoneurolysis: It is our hope that patients have a decrease in their acute and chronic postoperative pain (which might permit a decreased opioid consumption and opioid-related nausea/vomiting).

Possible benefits to others: Future patients may benefit if it is determined that cryoneurolysis decreases postoperative pain. In addition, with the opioid epidemic, any decrease in opioid requirements would be a welcome development.

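### The nausea item places vomiting at the top of a severity scale, so severity is lost for anyone who vomits, and a fall in nausea can be masked if vomiting does not fall with it

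*Combined protocol and SAP*

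**What the plan says.** The table of post-enrollment assessments in Section 9 contains the row "Nausea (0=none, 10=vomited", marked at postoperative-day contacts only. There is no row for vomiting. The outcome descriptions before the table do not mention nausea. They give no rule for scoring a subject with mild nausea who vomits, and no number of episodes that would count.

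Under Statistical Analysis in Section 9, "Differences between groups in demographic variables and secondary endpoints will be assessed with the Mann-Whitney U test for continuous or ordinal data", with Fisher's exact test for categorical data and box plots for display. Nausea falls under that sentence as a secondary ordinal endpoint. It is not the primary outcome: for mastectomy, "the primary outcome is the average NRS (as administered as part of the Brief Pain Inventory) queried on the afternoon of postoperative day 2". It is in no hypothesis in Section 6 and is not among the end points that Section 9 singles out for the other surgeries.

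Section 17 describes the hoped-for pain benefit of active treatment as one "which might permit a decreased opioid consumption and opioid-related nausea/vomiting".

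**The concern.** The plan's other 0-10 scales end at the worst degree of the thing they measure: the pain items at the worst pain, the interference items at complete interference. The nausea item changes subject at the top. On its face, a subject with slight nausea who vomits scores 10, while a subject with severe nausea all day who does not vomit scores 9 or less.

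Two things are at stake. The first is reporting. Severity is lost for those who vomit, and no later analysis can restore it. A difference between arms would not show whether nausea or vomiting had changed. A vomiting rate can be read off only if every 10 means vomiting, which the plan does not state. This matters because Sections 5 and 6 say the study is meant to supply data for powering later trials.

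The second is sensitivity. If nausea falls but vomiting does not, the scores of 10 in both arms dilute the contrast.

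**Working it through.** **Inputs.** The documents state no rate, effect size, power or sample size for nausea, so there is no nausea figure to reproduce. From the plan's pain calculation I borrow 30 per group ("n=30 patients per group provide 86% power"), two-sided 5%, and the SD of 2.5 used in its simulation. Whether that pain calculation is itself right is a separate question and does not affect this one. Assumed: sham mean nausea 3, active mean 1.5 (or 1, for a 2-point difference), and vomiting in 10-30% of sham subjects.

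**Model.** Severity S is a normal value, rounded and limited to 0-9. The combined score is C = 10 if the subject vomits, otherwise C = S. Each item is compared between arms by the two-sided Mann-Whitney test in simulated trials (3,000 to 4,000 per setting).

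**Why the result depends on vomiting.** The Mann-Whitney test responds to D = P(sham score higher) − P(active score higher) for a random pair. Let p_s and p_a be the vomiting probabilities under sham and active, unrelated to severity within an arm. Pairs in which neither vomits contribute (1 − p_s)(1 − p_a)·D. Pairs in which only one vomits contribute p_s(1 − p_a) − p_a(1 − p_s) = p_s − p_a. Pairs in which both vomit are tied. So

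D_combined = (1 − p_s)(1 − p_a)·D + (p_s − p_a).

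Ignoring rounding and limits, D = 2Φ(1.5 / (2.5√2)) − 1 = 2Φ(0.424) − 1 ≈ 0.329. With p_s = 0.20:

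- p_a = 0.20: 0.80 × 0.80 × 0.329 + 0 = 0.211
- p_a = 0.15: 0.80 × 0.85 × 0.329 + 0.05 = 0.274
- p_a = 0.10: 0.80 × 0.90 × 0.329 + 0.10 = 0.337

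With equal vomiting the signal shrinks by about a third. With vomiting halved it is slightly larger than on the severity item.

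**Simulated power, 1.5-point difference.**

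| Vomiting pattern | Separate severity item | Combined item |
|---|---|---|
| Equal in both arms, 10% | 57-60% | 42% |
| Equal in both arms, 20% | about 58% | about 29% |
| Equal in both arms, 30% | 57-60% | 18-20% |
| 20% falling to 15% | about 58% | about 43% |
| 30% falling to 22.5% | about 58% | 37-40% |
| Weakly linked to nausea (latent correlation 0.5) and falling with it, 20% | 58% | 48% |
| 20% halved to 10% | 57% | 61% |
| Occurs above a severity threshold, 20% | 57% | 57% |

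With equal rates, a within-arm latent correlation of 0.5 between nausea and vomiting changes almost nothing (57% to 29% at 20%). What drives the result is whether vomiting differs between arms.

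**Two-point difference, 20% vomiting.** The severity item has 82-83%. The combined item has 42-47% if vomiting is equal, 78% if it is halved and 81% under the threshold model.

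**Other checks.** With no effect on either component and 20% vomiting in both arms, the combined item rejects in 5.0% of trials. If vomiting is halved from 40% and severity is unchanged, the combined item has 29% power and a severity-only item 4%.

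**The case against.** The strongest reply is that the item is an ordinal nausea-and-vomiting composite with vomiting as the worst state. In a rank test a 10 is only the worst rank, so its distance from 9 carries no weight, and the median and quartiles of such a scale can be interpreted. Section 17 names nausea and vomiting together, as a possible consequence of lower opioid use, so the natural expectation is that both fall. In that case the combined item loses little or nothing, and it can pick up a fall in vomiting that a severity-only item would miss. No hypothesis depends on nausea. The case report form is not in the documents, so the one-episode reading rests on a short table label.

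Most of this stands. A reader might infer from the row that a real reduction in nausea will be masked, or that the Mann-Whitney comparison is meaningless. The documents support neither. Masking requires nausea to fall while vomiting falls clearly less, and no rates are given that would show this. The test is valid at its nominal level.

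Two things survive. The plan does not define the scale as a composite, and even as one it cannot show which component moved. Nor does the power loss require vomiting to be wholly unaffected: a reduction of a quarter still leaves a gap of about 15 points (58% against 43%).

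**Conclusion.** The point holds as a minor design weakness in a secondary outcome. What is certain from the text is that the single row does not record severity for subjects scored 10 for vomiting, and that the plan cannot report nausea and vomiting separately. What is conditional is the loss of power. At 20% vomiting and a 1.5-point difference it runs from about 29 points (58% to 29%) when vomiting is equal in the two arms to essentially none when vomiting is halved or follows severity. Every nausea and vomiting input behind those figures is assumed. The correct word is that a fall in nausea can be masked, not that it is. The primary outcome and the trial's main conclusions are untouched.

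**What to change.** Replace the row by two items at the same contacts: nausea on 0-10, with 0 = none and 10 = worst imaginable, and vomited since the last contact, yes or no. Compare severity with the Mann-Whitney test and vomiting with Fisher's exact test, both already named in Section 9. If the combined scale is wanted, define it in the plan as a composite with vomiting ranked worst; it can be derived from the two items.

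The cost is one yes/no question at calls already scheduled, a small change to the case report form, and two secondary comparisons where there was one. If the item cannot be changed, state that it is a composite, give the scoring rule for a subject who vomits, and do not report it as nausea severity.

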6. SPECIFIC AIMS

The ultimate objective of the proposed line of research is to determine if cryoanalgesia is an effective adjunctive treatment for pain in the period immediately following various painful surgical procedures; and, if this analgesic modality decreases the risk of persistent postoperative pain, or "chronic" pain. *The objective of the proposed pilot study is to optimize the protocol and collect data to power subsequent, definitive clinical trials.*

Specific Aim 1: To determine if, compared with current and customary analgesia, the addition of cryoanalgesia decreases the incidence and severity of post-surgical pain.

Hypothesis 1a (primary): The severity of surgically-related pain will be significantly decreased on postoperative day 2 with the addition of cryoanalgesia as compared with patients receiving solely standard-of-care treatment.

Hypothesis 1b: The incidence of chronic pain will be significantly decreased one year following surgery with the addition of cryoanalgesia as compared with patients receiving solely standard-of-care treatment.

Hypothesis 1c: The severity of chronic pain will be significantly decreased one year following surgery with the addition of cryoanalgesia as compared with patients receiving solely standard-of-care treatment.

[figure not shown]
Specific Aim 2: To determine if, compared with current and customary analgesia, the addition of cryoanalgesia improves postoperative functioning.

Hypothesis 2a: Following primary unilateral knee and shoulder arthroplasty as well as rotator cuff repair, joint range of motion will be significantly increased within the year following surgery with the addition of cryoanalgesia as compared with patients receiving solely standard-of-care treatment.

Hypothesis 2b: Following video-assisted thoracoscopic surgery, inspiratory spirometry will be improved within the month following surgery with the addition of cryoanalgesia as compared with patients receiving solely standard-of-care treatment.

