9. RESEARCH DESIGN AND METHODS

All subjects would continue to receive standard and customary postoperative analgesics, so there is no risk of subjects receiving a lower degree of analgesia than if they otherwise did not enroll in the study. The cryoneurolysis procedure will be done in addition to our current UCSD standard practice.

Study Overview

Day 0 Subjects randomized and cryoneurolysis/sham procedure administered

Days 0-4, 7, 14, 21 Pain levels, opioid consumption, and other end points collected [inspiratory spirometry for hospitalized subjects following video-assisted thoracoscopic surgery will occur at various time points as part of standard care and will be collected via EPIC]

Months 1, 3, 6, 12 Brief pain inventory administered [range-of-motion measurements following knee and shoulder arthroscopy as well as rotator cuff repair will occur at various time points as part of standard care and will be collected via EPIC]

Year 3 Cancer recurrence investigated for subjects with cancer-related procedures

Subjects will be individuals undergoing unilateral or bilateral mastectomy; upper or lower limb amputation; primary, unilateral total knee or shoulder arthroplasty; primary, unilateral rotator cuff repair; video-assisted thoracoscopic surgery; and burn-related skin grafting of the lateral thigh. Those who consent to participate in this study will have standard preoperative peripheral nerve blocks administered and catheters inserted: paravertebral blocks or a fascial plane block (e.g., erector spinae plane block) for mastectomy, femoral/sciatic for lower limb amputation, brachial plexus (or terminal nerves) for upper limb amputation; femoral or adductor canal for total knee arthroplasty; interscalene for shoulder arthroplasty or rotator cuff repair; thoracic epidural for video-assisted thoracoscopic surgery (VATS); and lateral femoral cutaneous nerve for skin grafting of the lateral thigh.

Treatment group assignment (randomization). Subjects with successfully-administered peripheral nerve blocks (defined by sensory changes in the appropriate nerve distribution) will be allocated to one of two possible treatments:

1. *cryoneurolysis*
2. *sham cryoneurolysis (placebo control)*

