Brief Pain Inventory: The Brief Pain Inventory (short form) is an instrument specifically designed to assess pain and its impact on physical and emotional functioning within the previous 24 hours.^{22,23} It has established reliability and validity, with minimal inter-rater discordance, and is recommended by

the Initiative on Methods, Measurement, and Pain Assessment in Clinical Trials (IMMPACT) consensus statement.²⁴ The Brief Pain Inventory is comprised of three domains: (1) *pain*, with four questions involving “worst”, “average”, “least”, and “current” pain levels using a 0-10 Numeric Rating Scale (NRS; 0 = no pain; 10 = worst pain imaginable); (2) percentage of *relief* provided by pain treatments with one question (reported score is the percentage divided by 10 and then subtracted from 10: 0 = complete relief, 10 = no relief); and, (3) *interference* with 7 questions involving physical and emotional functioning using a 0-10 Likert scale (0 = no interference; 10 = complete interference). The use of both single items (e.g., average pain) and the composite score (0 = optimal; 120 = worst possible) is supported by the IMMPACT recommendations for assessing pain in clinical trials.²⁵⁻²⁷

Opioid consumption

Sleep disturbances: due to surgical pain

Range of motion: measured with a standard goniometer

Forced expiratory volume in 1 second (FEV1): measured with a standard inspiratory spirometer

Cancer recurrence: for subjects who underwent the surgical procedure related to a primary cancer, subjects' records will be investigated for indications of cancer recurrence up to 3 years following catheter placement (including estrogen receptor status as + or -). Patients may be contacted by phone if records suggest that the patient has not returned to the original surgeon within the previous 12 months.

The questionnaire will differentiate among multiple dimensions of breast and limb pain:

Phantom pain: painful sensations referred to the lost body part (breast or limb).

Phantom breast/limb sensations: non-painful sensations referred to the lost body part.

Wound pain: painful sensations localized to the portion of the body still present.

Summary of post-enrollment assessments (color added for clarity)

Time Point:	Postoperative Days								Postoperative Months			
	0	1	2	3	4	7	14	21	1	3	6	12
Opioid consumption	•	•	•	•	•	•	•	•	•	•	•	•
Average & worst pain [NRS]	•	•	•	•	•	•	•	•				
Brief Pain Inventory									•	•	•	•
Average & worst phantom pain									•	•	•	•

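### Range of motion and FEV1, the main outcomes of interest in the knee, rotator cuff and VATS pilots, have no planned preoperative value, which costs precision and leaves later trials without a baseline-adjusted SD

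*Combined protocol and SAP*

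**What the plan says.** Under Statistical Analysis, Section 9 lists the outcomes that matter most in the pilot cohorts. Among them are "range-of-motion at 6 weeks for the rotator cuff repairs, range-of-motion for knee arthroplasty, and FEV1 for the VATS procedures". The same paragraph says that these cohorts are convenience samples meant to inform the power of later trials, and that they have no primary endpoint or statistical plan fixed in advance.

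The timing of both measures is given twice in Section 9:

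- The footnote to the assessment table says "joint range of motion will be measured at various time points between 1-12 months as part of standard postoperative care" and "FEV1 will be measured at various time points during hospitalization as part of standard postoperative care".
- The Study Overview refers to "inspiratory spirometry for hospitalized subjects following video-assisted thoracoscopic surgery" and to range of motion after joint surgery. It says of each that it "will occur at various time points as part of standard care and will be collected via EPIC".

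The table itself is headed "Summary of post-enrollment assessments". Its columns run from postoperative day 0 to month 12, with no preoperative column. No section lists a preoperative range of motion or FEV1, a change score, a percentage of the preoperative value, or a baseline covariate.

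On analysis, Section 9 says that "secondary endpoints will be assessed with the Mann-Whitney U test for continuous or ordinal data". Hypothesis 2a in Section 6 expects that "joint range of motion will be significantly increased within the year following surgery", relative to patients given standard care alone. Hypothesis 2b makes the same kind of comparison for spirometry after VATS.

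**The concern.** Joint motion and lung function vary between people before any operation. If the preoperative level predicts the postoperative level, an analysis that ignores it carries variation that could have been removed. In small arms, a chance difference in preoperative function then passes into the estimated effect, and no data are held to detect it or correct for it.

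The declared purpose of these cohorts sharpens the point. A pilot that feeds later sample-size calculations should deliver an SD and an effect estimate. Without preoperative values it can deliver only the unadjusted SD. It cannot estimate the correlation between the two time points, so it cannot say how much smaller a baseline-adjusted trial could be.

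**Working it through.** **Plan's own figure.** There is none for range of motion or FEV1. The only power figure in the plan concerns postoperative day 2 pain after mastectomy and does not bear on this point.

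**Inputs from the documents.** Section 10 allows 60 knee arthroplasty subjects, 60 VATS subjects, and 60 for shoulder arthroplasty and rotator cuff repair combined. Section 9 describes two arms.

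**Assumptions.**

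- Equal allocation, which gives 60 / 2 = 30 per arm for knee and for VATS.
- Half of the shared shoulder places go to rotator cuff repair: 30 subjects, or 15 per arm.
- Correlation r between preoperative and postoperative values of 0.3, 0.5, 0.7 or 0.8. The documents give none.
- No SD or target effect is given for these outcomes, so differences are in SD units, and 0.5 SD serves as an illustration.
- The two-sample t-test stands in for the Mann-Whitney test, at two-sided 5%. The small cost of estimating one covariate slope is ignored.

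**Precision.** ANCOVA on the preoperative value multiplies the outcome variance by 1 − r², so the interval width is multiplied by √(1 − r²). For r = 0.7, 1 − 0.49 = 0.51 and √0.51 = 0.714, which is 29% narrower. The ratio of the sample size needed without adjustment to that needed with it is 1/(1 − r²), here 1/0.51 = 1.96. The difference detectable with 80% power is 0.736 SD at 30 per arm and 1.060 SD at 15 per arm for raw values. Each is multiplied by √(1 − r²) after adjustment.

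| r | 1 − r² | Interval narrower by | Sample-size ratio | Detectable, 30 per arm | Detectable, 15 per arm | Power for 0.5 SD, 30 per arm |
|---|---|---|---|---|---|---|
| raw | 1 | – | 1.00 | 0.74 SD | 1.06 SD | 48% |
| 0.3 | 0.91 | 5% | 1.10 | 0.70 SD | 1.01 SD | 52% |
| 0.5 | 0.75 | 13% | 1.33 | 0.64 SD | 0.92 SD | 59% |
| 0.7 | 0.51 | 29% | 1.96 | 0.53 SD | 0.76 SD | 76% |
| 0.8 | 0.36 | 40% | 2.78 | 0.44 SD | 0.64 SD | 89% |

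**Chance imbalance.** The difference between arms in mean preoperative value has standard error √(2/n) in SD units: √(2/30) = 0.258 and √(2/15) = 0.365. The probability that it exceeds 0.3 SD in either direction is 2[1 − Φ(0.3/0.258)] ≈ 25% at 30 per arm and 2[1 − Φ(0.3/0.365)] ≈ 41% at 15 per arm. An imbalance of 0.3 SD shifts the outcome difference by r × 0.3. At r = 0.7 that is 0.21 SD, against a standard error of 0.26 SD for the raw comparison at 30 per arm.

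**Why not a change score.** Its variance factor is 2(1 − r). At r = 0.3 this is 1.4, worse than the raw value, and power for 0.5 SD at 30 per arm falls from 48% to 36%. It equals the raw value at r = 0.5. ANCOVA is no worse than either at any r, apart from the small cost noted above.

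**The case against.** Five arguments on the other side have weight.

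1. **The analysis is not specified.** A reader might infer that the plan commits to comparing raw values by Mann-Whitney. The documents do not support that as a fact. Section 9 disclaims a statistical plan for these cohorts, and the Mann-Whitney sentence follows the mastectomy sample-size text and speaks of secondary endpoints. Whether it governs these outcomes is unclear. This stands, but an analyst cannot adjust for a value that the plan does not say will be collected.

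2. **There is no bias.** A reader might infer that the missing baseline makes the comparison invalid. It does not. Allocation is randomized, with stratification by surgery type, and an unadjusted test already allows for chance imbalance in its standard error and type I error. This stands in full: the loss is one of precision.

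3. **Aim 2 does not require within-subject change.** Words such as increased and improved might suggest that it does. Hypotheses 2a and 2b both compare randomized groups, and postoperative values can answer them. This stands.

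4. **The gain may be small.** The documents give no correlation. Surgery alters the joint or lung, and unfixed measurement times add noise, so a low r is plausible. At r = 0.3 the interval narrows by only about 5%. The unadjusted SD is also not wrong to pass on: it sizes an unadjusted trial correctly and is conservative for an adjusted one. This stands, and is a reason for the pilot to estimate r.

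5. **The values may not exist or may not match.** The Study Overview says only that postoperative values come from EPIC. That preoperative values are recorded there is an assumption. Section 9 also pairs FEV1, an expiratory measure, with an inspiratory spirometer, and sets no time point for knee range of motion. Those gaps need their own resolution, and a baseline helps only if it measures the same quantity. This limits the gain but does not remove the case for using what is recorded.

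**Conclusion.** The concern holds as a matter of precision and of planning value, not of validity. The outcomes of main interest for three surgery types are scheduled only after surgery, and no preoperative value or baseline adjustment is listed. The powered mastectomy comparison is not affected.

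The size depends on an assumed correlation: the sample-size ratio runs from 1.10 at r = 0.3 to 2.78 at r = 0.8. The exposure to chance imbalance rests on 30 per arm for knee and VATS, and on an assumed 15 per arm for rotator cuff repair. The loss that does not depend on r is that the pilots, as written, cannot report the pre/post correlation or the adjusted SD at all.

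**What to change.** In the Study Overview and the assessment-table footnote of Section 9, add extraction from EPIC of the last preoperative range of motion (same joint and same movement) and of preoperative FEV1, where recorded. No new measurement is required. Record the date and, where known, the device.

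Under Statistical Analysis, state that these outcomes will be analysed by ANCOVA or rank ANCOVA on the preoperative value, alongside the unadjusted comparison. Handle absent baselines by single imputation, made without reference to treatment arm or outcome, or by a missing indicator. Report the pre/post correlation, the number of subjects with a preoperative value, and both the adjusted and the unadjusted SD.

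The cost is chart extraction from a system already in use, plus a few sentences of protocol text. The downside is that some values will be missing or come from a different device or date, which lowers the effective correlation and so the gain.

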Randomization will be stratified by surgery type (e.g., mastectomy, upper limb amputation, and lower limb amputation). Computer-generated randomization lists will be used to create sealed, opaque randomization envelopes with the treatment group assignment enclosed in each envelope labeled with the randomization number.

The specific nerves targeted will depend on the surgical site: intercostal nerves (4 levels depending on the specific surgical approach) for mastectomy; femoral/sciatic for lower limb amputation, brachial plexus (or terminal nerves) for upper limb amputation; infrapatellar branch of the saphenous nerve for knee arthroplasty; suprascapular nerve for shoulder surgery; intercostal nerves for VATS procedures, and the lateral femoral cutaneous nerve for skin grafting of the lateral thigh. The cryoneurolysis sites will be cleansed with chlorhexidine gluconate and isopropyl alcohol. Using the optimal ultrasound transducer for the specific anatomic location and subject anatomy (linear vs curvilinear array), the target nerves will be identified in a transverse cross-sectional (short axis) view.

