Cryoneurolysis probes are available for a console neurolysis device (PainBlocker, Epimed, Farmers Branch, Texas) that either (1) pass nitrous oxide to the tip inducing freezing temperatures; or, (2) vent the nitrous oxide at the base of the probe so that no gas reaches the probe tip, resulting in no temperature change. Importantly, these probes are indistinguishable in appearance, and therefore treating physicians, subjects, and all clinical staff will be masked to treatment group assignment [only the physician/investigator performing the cryoneurolysis will be unmasked]. An angiocatheter/introducer may be inserted beneath the ultrasound transducer and directed until the probe tip is immediately adjacent to the target nerve (lidocaine 2% will be administered, as needed, to anesthetize the angiocatheter track). The angiocatheter needle will be removed, leaving the angiocatheter through which the appropriate Epimed probe will be inserted until it is adjacent to the target nerve. The cryoneurolysis device will be triggered using 3 cycles of 2-minute gas activation (active or sham) separated by 1-minute defrost periods. For active probes, the nitrous oxide will be deployed to the tip where a drop in temperature to -70°C will result in cryoneurolysis. For the sham probes, the nitrous oxide will be vented prior to reaching the probe shaft, resulting in a lack of perineural temperature change. The process will be repeated with the same treatment probe for any additional nerves (e.g., all nerves will receive either active cryoneurolysis or sham/placebo, and not a mix of the two possible treatments).

FDA Approval. Cryoneurolysis has been FDA approved since May 28, 1976, with continuous clinical use since then. The specific device used for this study, the Epimed Painblocker, has been FDA cleared for use to treat both acute and chronic pain since April 30, 1986, as a significant risk device. The Painblocker is NOT considered experimental or investigational (there is no IDE); and, we are using the device in a manner that the FDA approved of regarding the subject population and purpose (treating acute pain).

Outcome measurements (end points). Staff blinded to treatment group assignment will perform all measures and assessments, which will include:

Pain: measured on the 11-point NRS of pain intensity

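### The skin-graft cohort's day-2 pain score names no body site, so it cannot separate pain at the treated lateral thigh from pain at any other graft wound

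*Combined protocol and SAP*

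**What the plan says.** All references are to the combined protocol and SAP.

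- **Population.** Section 9, Study Overview, includes "and burn-related skin grafting of the lateral thigh". Section 10 plans 60 such subjects. Neither section says whether the lateral thigh is the donor or the grafted site, or limits enrolment to subjects whose wounds all lie there.
- **Treatment.** The nerve to be frozen is "the lateral femoral cutaneous nerve for skin grafting of the lateral thigh". The standard block given to both arms targets the same nerve.
- **Endpoint.** Section 9, Statistical Analysis, puts this cohort among the pilots meant to inform the size of later trials, with no fixed primary endpoint or analysis plan. The endpoint of most interest is "average pain score on postoperative day 2 for shoulder arthroplasty and skin grafting subjects".
- **Measure.** Section 9, Outcome measurements, defines pain as "measured on the 11-point NRS of pain intensity". The assessment table has one row for average and worst NRS pain on days 0 to 21, not split by wound.
- **Site-specific items.** "The questionnaire will differentiate among multiple dimensions of breast and limb pain": phantom pain, phantom sensations and wound pain. In the table, phantom and wound pain appear only at months 1, 3, 6 and 12. Wound pain is defined in contrast to phantom pain, not as donor versus recipient wound.
- **Hypothesis.** Hypothesis 1a (section 6) concerns surgically related pain in general on day 2.

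**The concern.** The treatment acts on one nerve territory, but the score chosen to measure its effect is not tied to that territory. If a subject has a second painful wound elsewhere, the treatment cannot reach it, and its pain enters the score in both arms alike. The difference between arms then shrinks toward zero.

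No confirmatory test is at risk, because this cohort is a pilot. What is at stake is the planning estimate. The day-2 difference and SD are what the next trial would be sized on. If they come from a mixture of treated and untreated wounds, the effect of the nerve treatment will look smaller than it is. A single number per subject cannot be taken apart later, and the month-1 wound items come too late to help with day 2.

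**Working it through.** **No figure to reproduce.** The plan gives no SD, effect or power for skin grafting. The calculations below illustrate dilution; they do not check a stated number.

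**Inputs borrowed from the mastectomy cohort (section 9, Statistical Analysis):** difference 2 NRS points, SD 2.25, 30 per group, two-sided 5%. For skin grafting, 30 per arm is 60/2, which assumes equal allocation. The plan states 86% power for the mastectomy inputs. A two-sample t-test on them gives 92.3%, and 86.1% results at SD 2.5. That is a separate matter and does not affect this point.

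**Inputs not in the documents (assumed):** a second wound outside the lateral thigh, its pain level, the correlation between sites, and how a subject turns two sites into one answer.

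**Check 1: weighted score.** Let w be the share of the reported score that comes from the treated site. Then

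observed difference = w × 2

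n per arm for 86% power = 2 × 2.25² × (1.960 + 1.080)² / (observed difference)² ≈ 93.6 / (observed difference)²

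The SD is held at 2.25.

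| w | Observed difference | t-test power, 30 per arm | n per arm for 86% power |
|---|---|---|---|
| 1 | 2.0 | 92% | 24 |
| 0.75 | 1.5 | 72% | 42 |
| 0.5 | 1.0 | 40% | 94 |
| 0.25 | 0.5 | 13.5% | 375 |

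The required size grows as 1/w², so halving the treated site's share roughly quadruples it (24 to 94).

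**Check 2: simulated 0-10 scores.** Each subject has two correlated normal site scores (latent SD 2.25, correlation 0.5), rounded and clipped to 0-10. The thigh's latent means are 1.5 (active) and 3.5 (sham). The other site has the same latent mean in both arms. Arms of 30 are compared by Mann-Whitney.

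A thigh-specific score shows a difference of 1.7 points (less than 2 because of clipping at 0) and power of about 90%. For a single unsited score:

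| Other site's latent mean | Subject averages the sites: difference, power | Subject reports the worse site: difference, power |
|---|---|---|
| 0 | 0.9, 65% | 1.5, 83% |
| 1.5 | 0.9, 52% | 1.25, 64% |
| 3.5 | 0.9, 42% | 0.64, 21% |
| 5 | 0.9, 42% | 0.28, 8% |

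Repeat runs differ by a point or two of simulation error, so the ranges are about 41-65% for averaging and about 8-83% for the worse site. With the other site fixed at 3.5, varying the correlation from 0.2 to 0.7 moves power only from 38% to 50% (averaging) and from 16% to 27% (worse site). The other site's pain level therefore matters far more than the correlation under the worse-site rule.

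Both checks agree on direction: a second wound in the score shrinks the difference. They do not fix its size.

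**The case against.** Four points can fairly be made for the plan.

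1. **The second wound is not in the text.** No section mentions a donor site, a recipient site or a burn elsewhere. That a graft leaves two wounds is ordinary meaning, but the other wound's location and pain are unstated. If both wounds lie in the lateral thigh, dilution is small. This stands, and it is why the point is conditional.
2. **The protocol does not call the score overall.** A reader might infer that the investigators chose a whole-body score. The documents do not support that: they are silent on site, and no question script or case report form is among them. Nearby wording points to surgical pain (Hypothesis 1a, and sleep disturbance due to surgical pain). Even so, surgical pain would cover both wounds, so this does not confine the score to the thigh.
3. **Total surgical pain may be the right target.** Hypothesis 1a is about surgically related pain. For a later trial with that aim, the overall difference is the correct planning input, and a thigh-only score would overstate the benefit. This stands. It argues for collecting both scores, not for leaving the site unstated.
4. **The cohort is exploratory.** No primary endpoint or power is claimed for it, so the power figures serve only as a scale for the dilution. This stands and limits the seriousness of the point.

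**Conclusion.** The point holds in conditional form. As written, the day-2 score for skin grafting names no site, only one nerve is treated, and nothing else collected on day 2 separates pain by wound. If the other wound lies outside the lateral thigh and hurts, the treated-site effect is diluted in a way that cannot be undone after data collection.

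The size is not known. Under the mastectomy-based inputs, power of about 90% for a thigh-specific score becomes about 41-65% if subjects average the sites and about 8-83% if they report the worse site, as the other site's latent mean ranges from 0 to 5. These ranges rest on the assumed second wound, correlation 0.5, equal allocation, and a borrowed SD and effect.

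A reader might go further and say that the score measures mostly the untreated site, or that subjects will simply report their burn pain. The documents do not support either statement. With averaging, the treated site supplies half the score. With the worse-site rule, the loss is slight when the other wound hurts little.

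This is a gap in measurement for a pilot cohort, worth closing because it is cheap to close. It is not a flaw in a confirmatory test.

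**What to change.** For the skin-graft cohort only, at the existing day 0 to 21 contacts:

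- Ask average and worst NRS for the operated area of the lateral thigh, and ask the overall NRS as well.
- Record once per subject whether the lateral thigh is the donor or the grafted site.
- Report the day-2 difference and SD for both scores. State in section 9 that the thigh-specific score estimates the effect of the nerve treatment and the overall score addresses total surgical pain (Hypothesis 1a).

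The cost is one extra set of scores per contact and one checkbox, with no new visits, contacts or staff. The downside is small: the thigh score alone says less about the subject's total pain, which is why the overall score is kept beside it.
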